9.7. Genetics

A 6 mL whole blood sample for DNA isolation will be collected from participants who have consented to participate in the genetics analysis component of the study. Participation in the genetics analysis is optional. Participants who do not wish to participate in the genetic research may still participate in the study.

See [Appendix 6](#) for Information regarding genetic research. Details on procedures for collection and shipment and destruction of these samples can be found in the SRM.

9.8. Biomarkers

- Collection of samples for biomarker research is also part of this study. The following samples for biomarker research will be collected from all participants in this study as specified in the SoA:
 - peripheral venous blood samples for the preparation of serum and plasma
- Samples will be tested for biomarkers that are indicative of inflammation (i.e. CRP and fibrinogen), extracellular matrix turnover and remodelling to evaluate their association with the observed clinical responses or to help understand the underlying biological responses to danirixin.
- In addition, with the participant's consent, samples will be stored and may be used to investigate additional biomarkers thought to play a role in COPD disease progression or to evaluate their association with observed clinical responses to danirixin
- Samples also may be used for research to develop methods or support identification of prognostic/diagnostic biomarkers associated with clinical outcomes in COPD and related diseases.

9.9. Health Economics OR Medical Resource Utilization and Health Economics

Parameters for specific use in Health Economics analysis or Medical Resource Utilization and Health Economics are not evaluated in this study.

10. STATISTICAL CONSIDERATIONS

10.1. Hypothesis

The primary efficacy endpoint is the change from baseline of E-RS:COPD total score at month 6. The primary objective of the study is to study the dose response and select an appropriate dose for future drug development programs.

A model based probability inference approach in Bayesian framework will be used to guide decision-making around dose selection. The posterior probability of the change from baseline of E-RS:COPD for each active dose being less than placebo will be used.

10.2. Sample Size Determination

[figure not shown]
In order to evaluate the impact of different sample sizes, various simulations were undertaken to understand the following questions around the change in baseline of E-RS:COPD scores at 6 months:

- What is the 90% confidence interval half width for the estimate of the treatment effect of the 5 mg, 25 mg, 35 mg, and 50 mg doses?
- What is the probability that the point estimate of difference from placebo is less than -1.5 for the 5 mg, 25mg, 35mg and 50 mg doses?
- What is the probability that the two-sided 90% confidence interval of the treatment effect excludes 0 for 5 mg, 25 mg, 35 mg and 50 mg doses?
- What is the probability that the two-sided 90% confidence interval of the treatment effect difference from placebo excludes 0 for 5 mg, 25 mg, 35 mg and 50 mg doses?

There are 3 scenarios considered for the simulations, each based on different assumptions of the effect for each of the 6 treatment arms. No model assumptions were made to generate these values. The scenarios are found in [Table 4](#) and [Figure 2](#). The assumed between participant standard deviation is 6.5 which is based on interim data from the 200163 study. For each scenario, 10,000 iterations of simulations were run.

Table 4 Assumptions Used for Sample Size Calculations

	Scenario 1	Scenario 2	Scenario 3
Placebo	0	0	0
5 mg	-0.5	-0.333	-0.5
10 mg	-1	-0.667	-0.75
25 mg	-2	-1.333	-2
35 mg	-2.5	-1.667	-2
50 mg	-3	-2	-2

Figure 2 Simulation scenarios with best fit sigmoidal Emax model

The Emax model will be used for the primary analysis and was the basis for estimation of the simulated data. The more general 4 parameter version of this model is defined as:

$$y(\text{dose}) = E_0 + E_{\text{max}} \left[\frac{\text{dose}^m}{(ED_{50}^m + \text{dose}^m)} \right]$$

where $y()$ represents the E-RS:COPD change from baseline, E_0 is the mean response at dose = 0, E_{max} is the maximum dose effect (at dose = ∞), ED_{50} is the dose that yields a mean response of $E_0 + E_{\text{max}} / 2$, and m is the slope parameter allowing for sigmoidal dose response relationships.

Results of the sample size simulations are presented in [Figure 3](#), [Figure 4](#), [Figure 5](#) and [Figure 6](#), with the lowest danirixin dose (5 mg) and the 3 highest doses (25 mg, 35 mg, 50 mg).

Figure 3 Half width of the 90% confidence interval for the 5 mg, 25 mg, 35 mg and 50 mg doses

[figure not shown]

Figure 4 Proportion of simulations in which the point estimate of difference from placebo is less than -1.5 for doses of 5 mg, 25 mg, 35 mg and 50 mg

[figure not shown]

Figure 5 Proportion of simulations in which the 90% confidence interval excluded 0 for doses of 5 mg, 25 mg, 35 mg and 50 mg

[figure not shown]
[figure not shown]

Figure 6 Proportion of simulations in which the 90% confidence interval of difference from placebo excludes 0 for doses of 5 mg, 25 mg, 35 mg and 50 mg

Based on the simulations a sample size of at least $n = 600$ will allow for adequate precision in estimation of the 35 mg dose as well as sufficient proportion with 90% confidence interval difference from placebo excluding 0 (over 80% for the 35 mg dose under all scenarios) and proportion with 90% confidence interval of dose estimate excluding 0 (over 80% for all higher doses and scenarios except 25 mg under scenario 2).

10.2.1. Sample Size Re-estimation

At the time of the interim analysis for futility, sample size re-estimation may be considered by the study team if the assumptions driving the sample size calculations are shown to be incorrect (e.g., variability is higher than expected). No more than 100 additional participants will be considered.

10.3. Randomization

Participants will be randomized equally (1:1:1:1:1:1) to the six treatment arms of placebo, 5 mg, 10 mg, 25 mg, 35 mg and 50 mg danirixin. Randomization will be stratified by smoking status (current vs. former).

10.4. Populations for Analyses

For purposes of analysis, the following populations are defined:

Population	Description
All Participants	This population will comprise all participants screened and for whom a record exists on the study database and will be used for the tabulation and listing of reasons for withdrawal before randomization and listings of AEs and SAEs for nonrandomized participants.
Modified Intent To Treat (mITT)	
This population will comprise all participants randomized to treatment and who received at least one dose of study medication. Randomized subjects will be assumed to have received study medication unless definitive evidence to the contrary exists. A true Intent-to-treat analysis would use the randomized treatment, but this population will be ‘modified’ in that all data summaries and analyses for this population will be based on the actual treatment received, if it is different to the randomized treatment. This will constitute the primary population for all analyses of efficacy and safety.
 
If any subject received more than one treatment during a treatment period, their data will be reported according to the treatment they received for the longest period of time.

PK	This population will comprise all participants in the mITT population for whom a pharmacokinetic sample was obtained and analyzed while on treatment with DNX.

10.5. Statistical Analyses

Analysis methods for key endpoints are described below. Unless otherwise stated, all statistical testing will be two-sided and all confidence intervals or Bayesian credible intervals will be 90% two-sided.

Further details on all analyses will be described in the reporting and analysis plan (RAP).

10.5.1. Efficacy Analyses

10.5.1.1. Primary Analysis

The primary endpoint is 6 month change from baseline using the mITT population.

Baseline values of E-RS: COPD will be defined as the daily average of scores for the 7 days prior to randomization. Days with missing values will not count towards the average. A minimum of 4 days will be needed and participants without sufficient days will not be randomized.

Individual monthly E-RS:COPD means will be defined as the average E-RS:COPD scores during the following study days:

- Month 1: days 1-28
- Month 2: days 29-56
- Month 3: days 57-84
- Month 4: days 85-112
- Month 5: days 113-140
- Month 6: days 141-168

Days with missing values will not factor into the calculations. Participants will require a minimum number of 10 observations within a month, otherwise the monthly mean will be considered missing for that patient.

The primary analysis will be Emax (4 parameter) modeling of the dose-response curve for the primary efficacy endpoint of month 6 change from baseline. Smoking status will be included as a covariate in this model, allowing the asymptote values of the dose-response relation for smokers to differ from those of the non-smokers. This model formulation will require estimation of at most six parameters. Simpler models nested within this general formulation will be also considered, comprising formulations of the mean dose-response relation allowing for a fixed difference between smokers and non-smokers (parallel curves model), no difference between smokers and non-smokers and the Emax model restriction $m=1$. Model fitness will be measured using standard goodness of fit analysis. This analysis will allow for an assessment of the extent to which the variability of the trial data will be captured using the proposed model and what dose-response specification allows the best interpretation of the data.

The dose-response model will be fitted to the data using Bayesian techniques using the function uniform prior (FUP). The rationale for this choice of inference is that the FUP shrinks the dose-response towards a flat line throughout the dose range, therefore providing more conservative estimates of the dose-response relation compared to maximum likelihood.

Standard Bayesian diagnostic plots will be produced to aid in the interpretation of results. Based on the selected model, 90% two sided Bayesian credible interval for all treatment arms, all pairwise differences between each danirixin dose and placebo, as well as between active danirixin doses, will be generated.

Other models of dose response such as quadratic and log linear will be considered as alternative analysis option if the Emax model does not fit the data well. Similar analysis with the final model using the endpoint includes months 1-6 and months 3-6 will be fit. A longitudinal mixed effects model will be also be fit with dose as a categorical variable to explore the time trend of E-RS:COPD. Each of the three E-RS:COPD subscales (breathlessness, cough and sputum, and chest symptoms) will be analysed using similar methods for the primary analysis and longitudinal analysis. Details of these sensitivity analyses will be further described in the RAP.

10.5.1.2. Key Secondary Analyses

All analyses for other efficacy endpoints will use the mITT Population, unless otherwise noted. Dose will be treated as a categorical variable and no dose response modelling will be done unless otherwise stated. The treatment comparisons of interest will be between individual danirixin doses and placebo and between different danirixin doses. Smoking status (current vs former) will be included as a covariate in all analyses. All Bayesian analyses will use non-informative priors. Further details will be described in the RAP.

10.5.1.3. HCRU Exacerbations

The number of events associated with HCRU-defined exacerbations will be analyzed using generalised linear models assuming a negative binomial distribution for the underlying exacerbation rate with a log link and an offset to account for the length of time in study for each participant. The exacerbation rates for the danirixin and placebo groups, along with the ratio in exacerbation rates danirixin/placebo, will be estimated and corresponding 95% credible intervals will be produced.

10.5.1.4. Time to First HCRU Exacerbation

Time to first HCRU exacerbation will be defined from the date of randomization. Participants without an exacerbation and participants who withdraw from the study prior to any observed exacerbations will be censored at the time of last contact. Survival will be summarized by treatment groups through Kaplan-Meier curves. Treatment arms will be compared using a stratified log-rank test. Time to first severe HCRU exacerbation will be analysed in a similar manner.

10.5.2. Safety Analyses

All safety endpoints will be tabulated or plotted by treatment group and will be performed on the mITT Population. Further details will be described in the RAP.

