4. OBJECTIVES AND ENDPOINTS

Objectives	Endpoints

Primary
 
 • To characterize the dose response of danirixin compared with placebo on the incidence and severity of respiratory symptoms in participants with COPD • To compare the safety of danirixin with placebo in participants with COPD 	
 • Change from baseline in respiratory symptoms measured by E-RS:COPD daily diary at month 6: total score and subscales (i.e. breathlessness, cough and sputum, and chest symptoms) • Adverse events (AE), clinical laboratory values, vital signs, electrocardiogram (ECG)

Objectives	Endpoints

Secondary
 
 • To characterize the dose response of danirixin compared with placebo on the annual rate of moderate/severe COPD exacerbations in participants with COPD • To further characterize the clinical activity of danirixin compared to placebo in participants with COPD 	
 • Healthcare Resource Utilization (HCRU)-defined COPD exacerbations • E-RS:COPD Responder Analysis (including subscales) • Number of Exacerbations of Chronic Pulmonary Disease (EXACT) tool defined events • Time to first EXACT event • EXACT event severity • EXACT event duration for all events • Time to first HCRU-defined COPD exacerbation • Time to first severe HCRU-defined COPD exacerbation • HCRU-defined exacerbation duration • Change from baseline for the St. George's Respiratory Questionnaire (SGRQ) total score (derived from SGRQ-C) • SGRQ responder analysis • Change for baseline COPD Assessment Test (CAT) total score • CAT responder analysis • Lung function (FEV1, FEV1 % predicted, FVC, FEV1/FVC ratio) • Rescue medication use • Participant experience of physical activity (subset of approximately 50% of participants) measured using PROactive Clinic Visit Tool (C-PPAC)

Objectives	Endpoints

 To characterize the pharmacokinetics of danirixin in participants with COPD 	
 Danirixin concentration and standard pharmacokinetic parameters for danirixin (e.g. AUC, Cmax, Tmax), using dried blood spot data

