5. STUDY DESIGN

5.1. Overall Design

A study schematic is shown in [Figure 1](#). This is a parallel group study. Following screening and successful completion of the EXACT daily diary (all participants), rescue medication use daily diary (all participants) and PROactive baseline measurements (questionnaire and participant experience of physical activity) over study days -7 to 1, participants will be randomized (1:1:1:1:1) to receive one of five dose strengths of danirixin (5 mg, 10 mg, 25 mg, 35 mg and 50 mg) or placebo. Study treatment will be administered twice daily for 24 weeks. The PROactive baseline measurements will only be collected for those participants selected for the physical activity monitoring subgroup. Participants who do not properly complete (i.e. are not adherent with the requirements for completing and recording) the required baseline assessments (i.e. EXACT/E-RS:COPD daily diary, physical activity monitoring portion of PROactive, and daily rescue medication use baseline measurements) will not be randomized and will not be eligible for rescreening.

A minimum of three interim analyses are planned for the study. The first interim analysis will be an evaluation of danirixin pharmacokinetics after 10 participants in each treatment group participating in the PK substudy have completed Visit 3.

[figure not shown]
A futility analysis interim based on the E-RS:COPD endpoint and will be conducted after approximately 150 participants have completed 3 months of study treatment.

An additional interim analysis will be conducted approximately 12-15 months after the beginning of the study, or when 450 participants have completed 6 months of treatment, whichever is earlier. This interim analysis will be used to support GSK decisions regarding the further development of danirixin, and will include E-RS:COPD dose response modelling, secondary endpoints of HCRU-defined exacerbations and SGRQ total score along with all available safety data. No changes will be made to the study based on the results of this interim analysis.

Additional informal assessments of danirixin exposure and efficacy data may be undertaken during the conduct of the study as data becomes available. No decisions regarding study conduct will be made based on these informal assessments.

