5.2. Number of Participants

Approximately 700 participants will be screened to achieve approximately 600 randomized participants. It is anticipated that approximately 540 participants will complete 24 weeks of treatment and key study assessment (the dropout rate is estimated to be approximately 10% based on previous experience with studies enrolling similar participants).

For the analysis of study assessments, several analysis populations will be defined. Details of the evaluable participants for each planned analysis population are included in Section 10.4.

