3.6	3.13	mITT	AE1/AE3	Summary of On-treatment Adverse Events Leading to Permanent Discontinuation of Study Treatment or Withdrawal from Study by [System Organ Class and] Preferred Term	IDSL Use AE1 for interim with text in [] in title Use AE3 for final reporting with text in [] omitted.	StInt, SAC
3.7	3.14	mITT		Summary of On-treatment Adverse Events of Special Interest		StInt, SAC
	3.15	mITT		Summary of On-treatment Pneumonia (AE and SAE) by ICS	AE and SAE Subjects who have an event in the 'Infective pneumonia' SMQ By subjects receiving ICS for at least 7 days at the time on pneumonia onset.	Post SAC
Laboratory: Chemistry						
3.8	3.16	mITT	LB1	Summary of Chemistry Changes from Baseline	ICH E3, include change from baseline of min/max value	StInt, SAC
3.9	3.17	mITT	LB17	Summary of Worst Case Chemistry Results by Potential Clinical Importance Criteria	ICH E3	StInt, SAC
Laboratory: Hematology						
3.10	3.18	mITT	LB1	Summary of Hematology Changes from Baseline	ICH E3, include change from baseline of min/max value	StInt, SAC
3.11	3.19	mITT	LB17	Summary of Worst Case Hematology by Potential Clinical Importance Criteria	ICH E3	StInt, SAC

Safety: Tables						
StInt No.	SAC No.	Population	IDSL / Example Shell	Title	Programming Notes	Deliverable [Priority]
Laboratory: Hepatobiliary (Liver)						
3.12	3.20	mITT	LIVER1	Summary/Listing of Liver Monitoring/Stopping Event Reporting	IDSL – if there are very small number of events this summary will be replaced with a listing. Table title to be determined by content.	StInt, SAC
3.13	3.21	mITT	LIVER10	Summary/Listing of Hepatobiliary Laboratory Abnormalities	IDSL – if there are very small number of events this summary will be replaced with a listing. Table title to be determined by content.	StInt, SAC
ECG						
	3.22	mITT	EG1	Summary of ECG Findings	IDSL, include min/max value	SAC
	3.23	mITT	EG2	Summary of Change from Baseline in ECG Values by Visit	IDSL include change from baseline of min/max value	SAC
3.14	3.24	mITT	EG10	Summary of Maximum QTcF Values Post-Baseline Relative to Baseline by Category	IDSL	StInt, SAC
3.15	3.25	mITT	EG11	Summary of Maximum Increase in QTcF Values Post-Baseline Relative to Baseline by Category	IDSL	StInt, SAC
Vital Signs						
	3.26	mITT	VS1	Summary of Change from Baseline in Vital Signs	ICH E3, include change from baseline of min/max value	SAC
	3.27	mITT	VS7	Summary of Worst Case Vital Signs Results by Potential Clinical Importance Criteria	IDSL	SAC

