## 14.11.8. Safety Figures

Safety: Figures						
StInt No.	SAC No.	Population	IDSL / Example Shell	Title	Programming Notes	Deliverable [Priority]
Adverse Events						
	3.1	mITT	AE10	Plot of Common ( $\geq 5\%$ ) On-Treatment Adverse Events and Relative Risk	IDSL One page per active treatment compared to placebo Include AEs which have $\geq 5\%$ incidence in any treatment group	SAC
Laboratory						
3.1	3.2	mITT	LIVER14	Scatter Plot of Maximum Post-Baseline vs. Baseline for ALT	IDSL	StInt, SAC
3.2	3.3	mITT	LIVER9	Scatter Plot of Maximum Post-Baseline ALT vs. Maximum Post-Baseline Total Bilirubin	IDSL	StInt, SAC
3.3	3.4	mITT		Plot of Mean (95% CI) Neutrophil Counts over Time		StInt, SAC
	3.5	mITT		Plot of Mean (95% CI) Neutrophil Counts over Time for Subjects with Pneumonia		Post SAC
Spirometry						
	3.6	mITT		Mean (90% CI) Post-Bronchodilator FEV1 (L) over Time	Baseline, Day 84 and 168	Post SAC
3.4	3.7	mITT		Adjusted Mean (90% CI) Change from Baseline Post-Bronchodilator FEV1 (L) over Time		StInt, SAC
	3.8	mITT		Mean (90% CI) Post-Bronchodilator FVC (L) over Time	Baseline, Day 84 and 168	Post SAC
3.5	3.9	mITT		Adjusted Mean (90% CI) Change from Baseline Post-Bronchodilator FVC (L) over Time		StInt, SAC

Safety: Figures						
StInt No.	SAC No.	Population	IDSL / Example Shell	Title	Programming Notes	Deliverable [Priority]
	3.10	mITT		Mean (90% CI) Post-Bronchodilator FEV1/FVC Ratio over Time	Baseline, Day 84 and 168	Post SAC
ECG						
3.6	3.11	mITT		Boxplot of Change from Baseline in QTcF by Time and Treatment		StInt, SAC

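### Comparing safety with placebo is a primary objective, but the plan lists no danirixin-placebo estimate with an interval and no dose-trend summary for infective pneumonia or infections

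*Protocol*

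**What the plan says.** Protocol Section 4 lists "To compare the safety of danirixin with placebo in participants with COPD" as a primary objective beside the dose-response objective for symptoms. For the analysis, Protocol Section 10.5.2 says: "All safety endpoints will be tabulated or plotted by treatment group and will be performed on the mITT Population". It leaves further detail to the SAP.

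SAP Section 8 states an estimand for safety: the effect of the treatment actually received, in everyone randomised and dosed. Sections 8.1 to 8.3 then refer adverse events, events of special interest and laboratory data to sponsor display standards, without naming an estimator, an interval or a contrast. SAP Section 5.1 defines the reporting groups as placebo and five separate doses.

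Section 14.6.4 limits events of special interest to the infective pneumonia query. Their main display is Table 3.14, "Summary of On-treatment Adverse Events of Special Interest", and Table 3.15 splits pneumonia by inhaled corticosteroid use. The one listed adverse-event display that contrasts arms is safety Figure 3.1, a relative-risk plot described as "One page per active treatment compared to placebo". It is restricted to events with at least 5% incidence in some arm.

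**The concern.** An effect is declared as the target, but for the infection risk no quantity is named that would estimate it. Protocol Section 3.3.1 identifies impaired host defence as a potential risk and gives characterisation of infections such as pneumonia as part of the mitigation. A reader of the final report would have event counts in six columns and would have to judge by eye whether they differ from placebo or rise with dose.

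The two primary objectives are also treated differently. For symptoms, the sponsor fits a curve through all six arms and so uses the dose order. For infections, where events are likely to be sparser, the dose order enters no listed estimate of incidence.

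**Working it through.** **Inputs from the documents.** Size: "Approximately 700 participants will be screened to achieve approximately 600 randomized participants" (Protocol 5.2). Allocation: "Participants will be randomized equally (1:1:1:1:1:1) to the six treatment arms" (Protocol 10.3). So 600/6 = 100 per arm. Adverse events are analysed in all dosed participants, so 100 is used rather than the 90 per arm left after 10% dropout. Intervals are 90% two-sided (Protocol 10.5), which corresponds to a one-sided 5% rule.

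**The plan's own figure.** There is none for safety. For symptoms, Protocol 10.2 claims more than 80% for 35 mg versus placebo under every scenario. Simulating the Table 4 means with SD 6.5 and fitting Emax models gives 99%, 83–85% and 90–91% for scenarios 1 to 3, so the claim reproduces. The pairwise 35 mg contrast alone has SE = 6.5 × √(2/100) = 0.919 and power Φ(|δ|/0.919 − 1.645):

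- δ = −2.5: Φ(1.08) = 86%
- δ = −1.667: Φ(0.17) = 57%
- δ = −2: Φ(0.53) = 70%

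In scenarios 2 and 3, efficacy therefore passes 80% only by borrowing across doses.

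**Assumed safety rates.** The documents state no pneumonia or infection rate. For a linear rise, p(d) = p₀ + (p₅₀ − p₀) × d/50. With 2% to 8% this gives 2.0, 2.6, 3.2, 5.0, 6.2 and 8.0% for placebo, 5, 10, 25, 35 and 50 mg.

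**Tests.** These were run on 20,000 simulated trials of 6 × 100, rejecting when z > 1.645: a Cochran-Armitage trend on dose, and a two-proportion z-test of 50 mg versus placebo. A one-sided Fisher test is shown for reference. With no effect, both z-tests reject in roughly 5–6% of trials. Fisher rejects in only about 1.5–1.8% at a 3% event rate, so trend against Fisher is not a like-for-like comparison.

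| Assumed rates | Trend (z) | 50 mg vs placebo (z) | 50 mg vs placebo (Fisher) |
|---|---|---|---|
| 2% to 8%, linear | 80% | 67% | 48% |
| 2% to 6%, linear | 57% | 46% | 26% |

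**Pooling.** In the 2% to 8% case the mean rate over the five active arms is (2.6 + 3.2 + 5.0 + 6.2 + 8.0)/5 = 5.0%. Pooling therefore compares 5% with 2% instead of 8% with 2%. Its power is about 27% by Fisher (36% by z), below the single 50 mg contrast. If instead every dose carries 6% against 2%, pooling has about 43% by Fisher and the trend only about 21%. The two summaries suit different shapes of effect.

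**What an interval would show.** For 8 versus 2 events per 100, the half-width of the 90% interval is 1.645 × √(0.08 × 0.92/100 + 0.02 × 0.98/100) = 1.645 × 0.0305 = 5.0 points. The difference is 6 points, give or take 5, which bare counts do not convey.

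**Reach of Figure 3.1.** If pneumonia runs from 1% to 3%, some arm reaches 5% in only about 32% of simulated trials, even with all pneumonia counted as one term.

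**The case against.** The strongest reply is that the plan does more than tabulate and that descriptive safety reporting is normal in Phase II. Much of this stands.

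- A reader might infer that safety is only tabulated by arm and that dose order is never used. That is wrong. Figure 3.1 gives relative risks. FEV1 and FVC have model-based contrasts with placebo (SAP 8.4). Figure 5.2 plots neutrophils and CRP against trough concentration with placebo at zero and pneumonia cases highlighted. Protocol 10.5.3 allows PK/PD modelling of safety variables against exposure or dose if appropriate. However, none of these estimates pneumonia incidence by dose, the exposure plots are deliverables after the main analysis, and the modelling is conditional.
- A reader might infer that a missing all-danirixin column is why a dose-related signal would be lost. The arithmetic points the other way: pooling dilutes such a signal.
- A reader might infer that a signal would probably be missed. The documents give no event rate, and significance is not the plan's route to detection. A safety review team meets about every three months (Protocol 5.1), and the strategic interim covers pneumonia and other infections (Protocol 10.5.4.3). For common infections doubling from 15% or 20% at the top dose, the pairwise contrast already has 72% or 88% power (two-sided 5%).
- Mock shells are in a separate document (SAP 14.12), so an unlisted column cannot be ruled out.

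Descriptive reporting also fits a plan that adjusts for no multiplicity. Even so, an estimate with an interval is itself descriptive and requires no hypothesis test.

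**Conclusion.** The gap is real but narrow. For infective pneumonia, the infections system organ class and serious events, the documents list no danirixin-placebo estimate with an interval and no dose-trend summary, although the comparison is a primary objective and the SAP declares a treatment-effect estimand.

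The gain from a trend is moderate: about 13 points of power in the 2% to 8% case (80 − 67) and about 11 in the 2% to 6% case (57 − 46). The wider gap against Fisher, 80% versus 48%, should not be quoted as the gain, because Fisher works at a much smaller actual error rate. All of these figures rest on assumed rates, excess risk linear in dose, 100 per arm and a one-sided 5% rule.

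This is a low-cost improvement to reporting. It does not show that safety monitoring is inadequate or that a signal would go unseen.

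**What to change.** In SAP Section 8, and in or beside Tables 3.11 and 3.14, pre-specify for infective pneumonia, the infections system organ class and serious adverse events:

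1. the risk difference versus placebo for each dose, with a 90% interval;
2. one dose-trend estimate with a 90% interval, from logistic regression with dose continuous, or an exact Cochran-Armitage analysis if events are few;
3. a pooled danirixin-placebo risk difference, labelled as a secondary complement.

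Keep the by-dose columns.

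The cost is a few lines of SAP text and code and slightly more output, with no new data or visits. There are two limits to state alongside the results. The trend is weak when the excess is flat across doses (about 21% power for 2% versus 6%), and the pooled difference is weak when the excess rises with dose (about 27% by Fisher for 2% to 8%).
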